8.2.8. Slit-lamp Biomicroscopy

Biomicroscopic examinations will be performed using a slit-lamp. The examinations will include evaluation of the condition of the eyelids, conjunctiva, cornea, anterior chamber, and iris/pupil.

AGN-190584

Eyelid/Eyelid Margins/Lashes:Edema

0	(None)	=	No edema
+0.5	(Trace)	=	Localized, minimal (trace) swelling
+1	(Mild)	=	Localized, mild swelling
+2	(Moderate)	=	Diffuse, moderate swelling
+3	(Severe)	=	Diffuse, severe swelling

Erythema

0	(None)	=	No erythema
+0.5	(Trace)	=	Localized, minimal (trace) flush reddish color
+1	(Mild)	=	Localized, mild, flush reddish color
+2	(Moderate)	=	Diffuse reddish color encompassing the entire lid margin
+3	(Severe)	=	Deep diffuse reddish color of lid margins and superior and/or inferior eyelid

Conjunctiva (Bulbar):Hyperemia

0	(None)	=	No hyperemia
+0.5	(Trace)	=	Minimal (trace) flush, reddish color
+1	(Mild)	=	Mild flush, reddish color
+2	(Moderate)	=	Bright red color
+3	(Severe)	=	Deep, bright diffuse redness

Edema

0	(None)	=	No edema
+0.5	(Trace)	=	Localized, minimal (trace) swelling
+1	(Mild)	=	Localized, mild swelling
+2	(Moderate)	=	Diffuse, moderate swelling
+3	(Severe)	=	Diffuse, severe swelling

AGN-190584

Conjunctiva (Palpebral):Hyperemia

0	(None)	=	No hyperemia
+0.5	(Trace)	=	Minimal (trace) flush, reddish color
+1	(Mild)	=	Mild flush, reddish color
+2	(Moderate)	=	Bright red color
+3	(Severe)	=	Deep, bright diffuse redness

Edema

0	(None)	=	No edema
+0.5	(Trace)	=	Localized, minimal (trace) swelling
+1	(Mild)	=	Localized, mild swelling
+2	(Moderate)	=	Diffuse, moderate swelling
+3	(Severe)	=	Diffuse, severe swelling

Cornea:Edema

0	(None)	=	No edema
+0.5	(Trace)	=	Localized, minimal (trace) epithelial haze
+1	(Mild)	=	Dull glass appearance of epithelium that may include fine localized microcystic changes
+2	(Moderate)	=	Dull glass appearance of the epithelium with large number of cystic changes with or without stromal edema
+3	(Severe)	=	Epithelial bullae and/or stromal edema, localized or diffuse, with or without stromal striae

Superficial Punctate Keratopathy

0	=	No superficial punctate keratopathy
+0.5	=	Trace
+1	=	Mild
+2	=	Moderate
+3	=	Severe

Anterior Chamber:

The anterior chamber will be evaluated for pathology. If pathology is present, it will be described.

██████████
AGN-190584

Iris/Pupil:

The iris/pupil will be evaluated for pathology. If pathology is present, it will be described.

8.2.9. Manifest Refraction

Manifest refraction (distance and near) will be performed according to standard clinical practice in both mesopic and photopic conditions.

If a participant loses ≥ 1 line of CDVA or DCNVA compared with Hour 0 of the same study visit at Hour 1 after dosing, a manifest refraction should be repeated under the same lighting conditions.

Additional details are outlined in the Procedure Manual.

8.2.10. Dilated Funduscopy Examination

The fundus assessments should be conducted through a dilated pupil. The examinations will include evaluation of the lens, vitreous, fundus, and optic nerve. The C/D ratio will be assessed. The investigator should note if the pupil dilated normally.

Lens:**Lens Assessment:**

Use biomicroscopic examination, indirect lenses, direct/indirect ophthalmoscopy, etc., as appropriate, to visualize.

Lens Status:

The lens will be evaluated for pathology. If pathology is present, it will be described.

Cataract Assessment:

Under dilated examination, the presence and severity of nuclear, cortical, and posterior subcapsular cataract lens opacities will be evaluated. At the first dilated examination, each type of cataract, if present, will be graded using the scale below. At the last follow-up dilated examination, each type of cataract will be assessed for change from baseline and if changed, the current severity will be graded using the scale below:

- 0 = None
- +1 = Mild
- +2 = Moderate
- +3 = Severe

Vitreous:

The vitreous will be evaluated for pathology. If pathology is present, it will be described. It will be noted if the condition is not evaluable.

██████████
AGN-190584

Fundus:

The fundus (posterior pole; periphery, when dilated) will be evaluated for pathology. If pathology is present, it will be described. It will be noted if the condition is not evaluable.

Optic Nerve:

The optic nerve will be evaluated for pathology. If pathology is present, it will be described. It will be noted if the condition is not evaluable.

C/D Ratio:

C/D ratio will be reported using a 0.0 to 1.0 scale. It will be noted if the condition is not evaluable.

8.2.11. Suicidal Risk Monitoring

Suicidal risk monitoring is not applicable to this ophthalmology study.

8.3. Adverse Events and Serious Adverse Events

The definitions of an AE or SAE can be found in [Appendix 2](#).

AEs will be reported by the participant (or, when appropriate, by a caregiver, surrogate, or the participant's legally authorized representative).

The investigator and any qualified designees are responsible for detecting, documenting, and recording events that meet the definition of an AE or SAE and remain responsible for following up AEs that are serious, considered related to the study intervention or study procedures, or that caused the participant to discontinue the study intervention (ie, repeat treatment) or study (see [Section 7](#)).

8.3.1. Time Period and Frequency for Collecting Adverse Event and Serious Adverse Event Information

All SAEs from the signing of the ICF until 30 days after the last dose of study intervention will be collected at the timepoints specified in the SoA ([Section 1.3](#)), and as observed or reported spontaneously by study participants.

All AEs from the signing of the ICF until 30 days after the last dose of study intervention will be collected at the timepoints specified in the SoA ([Section 1.3](#)), and as observed or reported spontaneously by study participants.

Medical occurrences that begin before the start of study intervention, but after obtaining informed consent will be recorded in the AE section of the eCRF.

All SAEs will be recorded and reported to the sponsor or designee within 24 hours, as indicated in [Appendix 2](#). The investigator will submit any updated SAE data to the sponsor within 24 hours of it being available.

██████████
AGN-190584

Investigators are not obligated to actively seek AE or SAE information after conclusion of the study participation. However, if the investigator learns of any SAE, including a death, at any time after a participant has been discharged from the study, and he/she considers the event to be reasonably related to the study intervention or study participation, the investigator must promptly notify the sponsor.

The methods of recording, evaluating, and assessing causality of AEs and SAEs and the procedures for completing and transmitting SAE reports are provided in [Appendix 2](#).

8.3.2. Method of Detecting Adverse Events and Serious Adverse Events

Care will be taken not to introduce bias when detecting AEs and/or SAEs. Open-ended and non-leading verbal questioning of the participant is the preferred method to inquire about AE occurrences.

8.3.3. Follow-up of Adverse Events and Serious Adverse Events

After the initial AE/SAE report, the investigator is required to proactively follow each participant at subsequent visits/contacts. All AEs/SAEs will be followed until resolution, stabilization, the event is otherwise explained, or the participant is lost to follow-up (as defined in Section 7.3).

The investigator is obligated to perform or arrange for the conduct of supplemental measurements and/or evaluations as medically indicated or as requested by Allergan to elucidate the nature and/or causality of the AE or SAE as fully as possible. This may include additional laboratory tests or investigations, histopathological examinations, or consultation with other health care professionals.

If a participant dies during participation in the study, the investigator will provide Allergan with a copy of any postmortem findings including histopathology.

If a participant is hospitalized and discharged, follow-up attempts must be made to obtain the discharge summary from the hospital and, if obtained, it should be sent to the sponsor.

New or updated information will be recorded in the originally completed eCRF.

The investigator will submit any updated SAE data to Allergan within 24 hours of receipt of the information.

8.3.4. Regulatory Reporting Requirements for Serious Adverse Events

- Prompt notification by the investigator to the sponsor of an SAE is essential so that legal obligations and ethical responsibilities towards the safety of participants and the safety of a study intervention under clinical investigation are met.
- The sponsor has a legal responsibility to notify both the local regulatory authority and other regulatory agencies about the safety of a study intervention under clinical investigation. The sponsor will comply with country-specific regulatory requirements relating to safety reporting to the regulatory authority, IRBs/IECs, and investigators.

AGN-190584

- Investigator safety reports must be prepared for suspected unexpected serious adverse reactions according to local regulatory requirements and sponsor policy and forwarded to investigators as necessary.
- An investigator who receives an investigator safety report describing an SAE or other specific safety information (eg, summary or listing of SAEs) from the sponsor will review and then file it along with the IB and will notify the IRB/IEC, if appropriate according to local requirements.

8.3.5. Pregnancy

- If a pregnancy is confirmed after the participant has received the study intervention, the participant may choose to exit the study after appropriate safety follow-up or to remain in the study for all safety and efficacy follow-up assessments through the EOS visit.
- Details of all pregnancies in female participants and, if indicated, female partners of male participants will be collected after the start of study intervention and through the duration of the pregnancy.
- If a pregnancy is reported, the investigator should inform Allergan within 24 hours of learning of the pregnancy and should follow the procedures outlined in [Appendix 6](#).
- Abnormal pregnancy outcomes (eg, spontaneous abortion, fetal death, stillbirth, congenital anomalies, ectopic pregnancy) or genetic abnormalities (whether leading to an elective abortion or not) are considered SAEs.

8.3.6. Medication Errors

Medication error refers to any unintended error in the dosing and/or administration of the study intervention as per instructions in the protocol. Medication errors generally fall into 4 categories as follows:

- Wrong study drug
- Wrong dose (including dosing regimen, strength, form, concentration, amount)
- Wrong route of administration
- Wrong participant (ie, not administered to the intended participant)

8.4. Treatment of Overdose

Treatment of overdose is not applicable to this ophthalmology study.

██████████
AGN-190584

8.5. Pharmacokinetics

Pharmacokinetic parameters are not evaluated in this study.

8.6. Pharmacodynamics

Pharmacodynamic parameters are not evaluated in this study.

8.7. Genetics

Genetics are not evaluated in this study.

8.8. Biomarkers and Other Assessments

8.8.1. Biomarkers

Biomarkers are not evaluated in this study.

8.8.2. Determination of Dominant Eye

Participants will be asked to extend their arms out in front of them at eye level, with their palms facing away, fingers together, and facing upward. Participants will bring their hands together, forming a small window by overlapping their thumbs and overlapping their fingers. Participants will select a small object at least 10 feet in front of them and look at it with both eyes through the view window in their hands. While remaining focused on the object, participants will close the right eye and take note of whether the image remains visible. If the image remains visible, the left eye is the dominant eye. If the image is no longer visible, the right eye is the dominant eye. This will be confirmed by closing the left eye and taking note of whether the image remains visible. Details will be outlined in the Procedure Manual.

8.9. Health Economics

██████████ PRO instruments (questionnaires) are administered in this study ██████████

At screening, participants will answer questions on vision functioning and health-related quality of life using the NEI VFQ-25, including the near vision subscale items (Questions A3 to A5) from the Appendix of Optional Additional Questions.

Each participant will also perform four different near vision reading tasks under mesopic and photopic conditions. Participants will subsequently rate their vision-related reading ability, and satisfaction with their vision-related reading ability on the NVPTQ.

Participants will also answer questions measuring overall satisfaction with the treatment using ██████████ questions assessing the impact of presbyopia on their life – and need for compensatory coping mechanisms – using the PICQ.

AGN-190584

Health care resource utilization outcomes are not evaluated in this study.

For additional detail on PRO assessments, please see the [PRO Assessments Manual](#).

9. Statistical Considerations

9.1. Statistical Hypotheses

The null and alternative hypotheses for the primary efficacy endpoint are:

- H_0 : AGN-190584 ophthalmic solution and vehicle dosed bilaterally, once daily for 30 days have the same effect in the proportion of participants gaining 3 lines or more in mesopic, high contrast, binocular DCNVA at Day 30, Hour 3;
- H_A : AGN-190584 ophthalmic solution and vehicle dosed bilaterally, once daily for 30 days do not have the same effect in the proportion of participants gaining 3 lines or more in mesopic, high contrast, binocular DCNVA at Day 30, Hour 3.

The null and alternative hypotheses for the key secondary efficacy endpoint are:

- H_0 : AGN-190584 ophthalmic solution and vehicle dosed bilaterally, once daily for 30 days have the same effect in the proportion of participants gaining 3 lines or more in mesopic, high contrast, binocular DCNVA at Day 30, Hour 6;
- H_A : AGN-190584 ophthalmic solution and vehicle dosed bilaterally, once daily for 30 days do not have the same effect in the proportion of participants gaining 3 lines or more in mesopic, high contrast, binocular DCNVA at Day 30, Hour 6.

9.2. Sample Size Determination

The primary efficacy endpoint is the proportion of participants gaining 3 lines or more in mesopic, high contrast, binocular DCNVA at Day 30, Hour 3. The key secondary efficacy endpoint is the proportion of participants gaining 3 lines or more in mesopic, high contrast, binocular DCNVA at Day 30, Hour 6. The sample size calculation is based on the key secondary efficacy endpoint. The vehicle group intervention effect was 8.8% and the AGN-190584 effect was 18.4% in the first Phase 3 Study 1883-301-013. Assuming the same underlying response rates for Study 1883-302-013, approximately 200 participants will be required in each study intervention group to detect the above difference with a power of 80% or greater at the 2-sided 5% significance level.

AGN-190584

9.3. Populations for Analyses

The analysis populations will consist of participants as defined below:

- The ITT population includes all randomized participants. Participants will be summarized according to the randomized study intervention.
- The safety population includes all treated participants who receive ≥ 1 administration of study intervention. Participants will be summarized according to the study intervention they actually received.

9.4. Statistical Analyses

The SAP will be developed and finalized before database lock and unmasking and will describe the participant populations to be included in the analyses, and procedures for accounting for missing, unused, and spurious data. This section is a summary of the planned statistical analyses of the primary and secondary endpoints.

9.4.1. Efficacy Analyses

The efficacy analyses will be based on the ITT population. Baseline for efficacy is defined as the last nonmissing efficacy assessment before the first dose of study intervention. All statistical tests will be 2-sided hypothesis tests performed at the 5% level of significance for main effects. All confidence intervals will be 2-sided 95% confidence intervals, unless stated otherwise.

9.4.1.1. Analysis Endpoints

The primary and secondary efficacy endpoints are listed below and analyses will be described in the following sections. The analyses for other efficacy endpoints listed below will be described in the SAP.

Primary Efficacy Endpoint:

- Proportion of participants gaining 3 lines or more in mesopic, high contrast, binocular DCNVA at Day 30, Hour 3.

Key Secondary Efficacy Endpoint:

- Proportion of participants gaining 3 lines or more in mesopic, high contrast, binocular DCNVA at Day 30, Hour 6.

Secondary Efficacy Endpoints:

1. Proportion of participants gaining 3-lines or more in mesopic, high contrast, binocular, DCNVA at Day 30, Hour 8.
2. Change from baseline mesopic, high contrast, binocular DCNVA letters at Day 30, Hour 0.5.

AGN-190584

3. Proportion of participants achieving 20/40 or better in photopic, high contrast, binocular, DCNVA at Day 30, Hour 1.
4. Mesopic NVPTQ Performance score mean change from baseline at Day 30, Hour 3.
5. Change from baseline photopic, high contrast, binocular DCIVA letters at Day 30, Hour 3.
6. Proportion of participants gaining 3-lines or more in mesopic, high contrast, binocular, DCNVA at Day 30, Hour 10.
7. Change from baseline mesopic, high contrast, binocular DCNVA letters at Day 30, Hour 0.25.
8. Proportion of participants achieving 20/40 or better in photopic, high contrast, binocular, DCNVA at Day 30, Hour 3.
9. Mesopic NVPTQ Satisfaction score mean change from baseline at Day 30, Hour 3.
10. PICQ Coping score mean change from baseline at Day 30, Hour 3.
11. PICQ Impact score mean change from baseline at Day 30, Hour 3.

9.4.1.2. Primary Analyses

The proportion of participants gaining 3 lines or more in mesopic, high contrast, binocular DCNVA at Day 30, Hour 3 will be analyzed using chi-square test. Missing data will be regarded as 3-line gain failure.

9.4.1.3. Secondary Analyses

The key secondary efficacy endpoint is the proportion of participants gaining 3 lines or more in mesopic, high contrast, binocular DCNVA at Day 30, Hour 6.

The key secondary efficacy endpoint will be analyzed using a chi-square test. Missing data will be regarded as 3-line gain failure.

All analyses for other secondary efficacy endpoints will be based on observed data only. Secondary endpoints 1, 3, 6, and 8 will be analyzed using a chi-square test. Secondary endpoints 2, 4, 5, and 7 will be analyzed using MMRM with study intervention group, visit, visit by study intervention group interaction, age group, baseline binocular DCNVA severity, iris color, emmetropes/non-emmetropes, baseline value, and baseline value by visit interaction as fixed effects. The within-participant correlation error structure is unstructured. Secondary endpoints 9, 10, and 11 will be analyzed using analysis of covariance with study intervention group, age group, baseline binocular DCNVA severity, iris color, emmetropes/non-emmetropes, and baseline domain score as fixed effects.

AGN-190584

To control the overall Type 1 error rate in the efficacy analysis, a gatekeeping testing procedure will be used. Secondary efficacy endpoints will be tested only if the primary efficacy endpoint is statistically significant. A proper multiple comparison procedure will be pre-specified in the SAP.

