6.3. Measures to Minimize Bias: Randomization and Blinding

All participants will be centrally assigned to randomized study intervention using the IxRS. Randomization and kit assignment will be conducted on Day 1 (baseline). At Day 1, participants will be randomized in a 1:1 ratio into 1 of the 2 study groups. This randomization will be stratified by age (2 groups: ≤ 50 years and > 50 years), baseline binocular DCNVA (2 groups: 20/40 to 20/60 inclusively, and worse than 20/60), iris color (brown and non-brown), and emmetropes/non-emmetropes. A maximum of 50% (100 per arm) of the participants enrolled will have brown iris color, and a maximum of 25% (50 per arm) of the participants will be non-emmetropes (a sphere outside of -0.50 D to +0.75 D and/or a cylinder greater than 0.75 D).

AGN-190584

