**5.4.2. Other Secondary Analyses**

Other secondary efficacy endpoints include:

1. Proportion of participants gaining 3-lines or more in mesopic, high contrast, binocular, DCNVA at Day 30, Hour 8.
2. Change from baseline in mesopic, high contrast, binocular DCNVA letters at Day 30, Hour 0.5.
3. Proportion of participants achieving 20/40 or better in photopic, high contrast, binocular, DCNVA at Day 30, Hour 1.
4. Change from baseline in Mesopic NVPTQ Performance score at Day 30, Hour 3.
5. Change from baseline in photopic, high contrast, binocular DCIVA letters at Day 30, Hour 3.
6. Proportion of participants gaining 3-lines or more in mesopic, high contrast, binocular, DCNVA at Day 30, Hour 10.
7. Change from baseline in mesopic, high contrast, binocular DCNVA letters at Day 30, Hour 0.25.
8. Proportion of participants achieving 20/40 or better in photopic, high contrast, binocular, DCNVA at Day 30, Hour 3.
9. Change from baseline in Mesopic NVPTQ Satisfaction score at Day 30, Hour 3.
10. Change from baseline in PICQ Coping score at Day 30, Hour 3.
11. Change from baseline in PICQ Impact score at Day 30, Hour 3.

All secondary endpoints related to proportion of participant gaining 3 lines or more or achieving 20/40 better (endpoints 1, 3, 6 and 8) will be analyzed with the same analysis method as the primary efficacy parameter.

Timepoints are defined as scheduled measurement times made for each visit. Change from baseline in mesopic, high contrast, binocular DCNVA letters (endpoints 2 and 7) will be analyzed using mixed-effects model with repeated measures (MMRM) by timepoint that includes treatment, visit, treatment by visit interaction, age group, baseline DCNVA severity, iris color, and emmetropes/non-emmetropes as factors as well as baseline DCNVA value, and baseline DCNVA value by visit interaction as covariates under the assumption of missing at random (MAR). An unstructured covariance matrix will be used as the covariance structure for

AGN-190584

repeated measurements. A sensitivity analysis will be implemented with the missing data imputed with the average outcome of the vehicle arm under the assumption of missing not at random (MNAR). Change from baseline in photopic, high contrast, binocular DCIVA letters (endpoints 4) will be analyzed with the similar way as change from baseline in mesopic, high contrast, binocular DCNVA letters. Baseline DCIVA will be included as the covariate instead of baseline DCNVA.

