NVPTQ and PICQ scoring algorithms are provided in [Appendix 4](#). Change from baseline in the mesopic NVPTQ Performance score, Mesopic NVPTQ Satisfaction score, PICQ Coping score, and PICQ Impact score (endpoints 4, 9, 10 and 11) will be analyzed using an analysis of covariance (ANCOVA) model that includes treatment, age group, baseline DCNVA severity, iris color, emmetropes/non-emmetropes as factors as well as baseline PRO score as covariate. Also, the cumulative distribution function (CDF) curves will be presented for each of the change from baseline PRO domain scores. The CDF curves (one per domain score for a total of four) represent the cumulative proportion of patients with any particular level of CFB in PRO domain scores at Day 30 Hour 3, by treatment arm. Curves will be produced with a vertical line drawn at the responder threshold.

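### The questionnaire models carry baseline near acuity only as a two-level stratum; adding the measured mesopic letter score, chiefly for the two NVPTQ endpoints, is an optional and probably small gain in precision

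*Protocol*

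**What the plan says.** Protocol 9.4.1.3 analyses NVPTQ Satisfaction, PICQ Coping and PICQ Impact (endpoints 9, 10 and 11) by "analysis of covariance with study intervention group, age group, baseline binocular DCNVA severity, iris color, emmetropes/non-emmetropes, and baseline domain score as fixed effects". NVPTQ Performance (endpoint 4) is treated differently there: "Secondary endpoints 2, 4, 5, and 7 will be analyzed using MMRM", a model with the same stratification factors, the endpoint's own baseline value and its interaction with visit.

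SAP 5.4.2 puts all four questionnaire endpoints (H5, H9, H10 and H11 in Table 5-1) into one ANCOVA, with treatment, age group and "baseline DCNVA severity, iris color, emmetropes/non-emmetropes as factors as well as baseline PRO score as covariate".

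The DCNVA severity term follows the randomisation stratum in Protocol 6.3: "baseline binocular DCNVA (2 groups: 20/40 to 20/60 inclusively, and worse than 20/60". The DCNVA letter models in SAP 5.4.2 have the same strata "as factors as well as baseline DCNVA value, and baseline DCNVA value by visit interaction as covariates".

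Protocol Table 8-1 schedules mesopic binocular DCNVA at screening and at Day 1, Hour 0. The continuous value is therefore in hand before the first dose.

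**The concern.** The mesopic NVPTQ asks participants to read four texts in dim light and rate how they did. Mesopic binocular DCNVA is the closest measured physical counterpart, yet the NVPTQ models see it only as better or worse than one cut point.

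The baseline NVPTQ score need not absorb the rest, because its scoring is coarse. In SAP Appendix 4, Table 1, a Performance testlet is 0 both for a participant who could read nothing and for one who rated the task poor with helpful squinting. Table 2 merges the two lowest satisfaction answers in the same way when squinting helped. Participants with different acuity can therefore share a baseline score.

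Only precision is at stake. If the letter score predicts the Day 30 score beyond what is already in the model, leaving it out widens the interval and costs some power. This matters most for H5, which starts at alpha 0.01, and for H9, which must be rejected before H10 and H11 are tested. No sizing was done for any questionnaire endpoint.

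**Working it through.** **1. The plan's own figure.** Protocol 9.2 and SAP 3 size the trial on the key secondary responder endpoint: 8.8% against 18.4%, two-sided 5%, 80% power. With pooled variance under the null and no continuity correction:

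n = [1.960 × √(2 × 0.136 × 0.864) + 0.842 × √(0.088 × 0.912 + 0.184 × 0.816)]² / 0.096² = 199 per arm.

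At 200 per arm the power is 80.2%, so the stated figure reproduces. It says nothing about the questionnaires: neither document gives an SD, an effect size or a power for them.

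**2. What each model contains.**

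| Endpoint | Protocol 9.4.1.3 | SAP 5.4.2 | Near acuity in model | Own baseline score | Level stated in SAP 5.4.3 |
|---|---|---|---|---|---|
| NVPTQ Performance (H5) | MMRM | ANCOVA | stratum only | yes | 0.01 |
| NVPTQ Satisfaction (H9) | ANCOVA | ANCOVA | stratum only | yes | none in the text |
| PICQ Coping (H10) | ANCOVA | ANCOVA | stratum only | yes | none in the text |
| PICQ Impact (H11) | ANCOVA | ANCOVA | stratum only | yes | none in the text |

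The absence of the letter score holds for all four endpoints under either document.

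**3. Gain if the letter score is added.** Let r be the partial correlation of baseline letters with the Day 30 score, given every covariate already in the model. Residual variance is multiplied by 1 − r². The equivalent increase in size is 200/(1 − r²) − 200 per arm. Starting from power P at two-sided alpha 0.01:

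new power = Φ[(2.576 + z_P)/√(1 − r²) − 2.576].

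The documents give neither r nor P. Both are assumed.

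| r | variance reduction | equivalent extra per arm | from 80% | from 60% |
|---|---|---|---|---|
| 0.1 | 1% | 2 | 80.5% | 61% |
| 0.2 | 4% | 8 | 81.9% | 62% |
| 0.3 | 9% | 20 | 84.3% | 65% |

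Example for r = 0.3 from 80%: (2.576 + 0.842)/√0.91 − 2.576 = 1.007, and Φ(1.007) = 84.3%.

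**4. The same r, defined before the stratum is removed.** Suppose instead that r is conditional on the baseline questionnaire score only, and that the stratum is a cut of a normally distributed letter score. A 50/50 split keeps a fraction k = 0.637 of the linear information, and a 20/80 split keeps 0.490. The extra variance explained is 1 − (1 − r²)/(1 − k r²).

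| r | extra variance explained | power from 80% at 0.01 |
|---|---|---|
| 0.1 | 0.4% to 0.5% | 80.2% |
| 0.2 | 1.5% to 2.1% | 80.7% to 81.0% |
| 0.3 | 3.5% to 4.8% | 81.7% to 82.3% |
| 0.5 | 10.8% to 14.5% | 85.1% to 86.9% |

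On this definition a gain of five points needs r of about 0.5.

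**5. Simulation does not settle the size.** With an acuity-score correlation of 0.2 to 0.6 and occasion-to-occasion noise, the variance reduction was about 0.2% to 3%. With four floored items driven by a trait shared with acuity, it was about 3% to 16%. The answer follows the assumed link, and the documents do not report that link.

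**The case against.** The strongest reply is that the plan is consistent. It adjusts every continuous endpoint for the strata and that outcome's own baseline. The DCIVA model replaces baseline DCNVA with baseline DCIVA on the same rule, so the questionnaire models have not been treated worse than the letter models. The outcome's own baseline would be expected to be the main precision covariate, and it is already there. This stands: the omission is neither an inconsistency nor an error.

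Three stronger readings are tempting, and the documents do not support them.

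- A reader might infer that all four questionnaire tests run at alpha 0.01. SAP 5.4.3 gives 0.01 to the key secondary endpoint, H2, H3, H4 and H5, and only H5 is a questionnaire endpoint. H9, H10 and H11 come later in the graph, at levels the visible text does not state.
- A reader might carry the floor argument over to the PICQ. A zero there means never or not at all, and items cover coping behaviour such as use of glasses. Nothing shows that distance-corrected acuity adds much to the PICQ's own baseline. Even for the NVPTQ, a total of zero requires every non-missing testlet to be zero.
- A reader might infer that the screening NEI VFQ-25 near-vision items are also wasted and should be added. No size can be put on that. Health economics and exploratory questionnaire analyses have separate plans, and the text of SAP 5.7.1 is not in the public document. That addition is not proposed.

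It is also fair that the benefit rests on an assumed correlation and may be under one power point. What remains is that a relevant baseline value is collected and costs almost nothing to use.

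**Conclusion.** The point holds as an optional refinement. The planned questionnaire analyses are valid: omitting a further prognostic covariate does not bias the randomised comparison or inflate type I error.

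The possible gain runs from a fraction of a power point to about four points, from an assumed 80% start at alpha 0.01, for partial correlations up to 0.3. The lower part of that range is the more plausible, because the baseline score and the stratum already absorb much of what acuity could explain. The case is most direct for the two mesopic NVPTQ endpoints and weaker for the PICQ. A material loss of power is not shown and cannot be shown from these documents.

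One related matter needs correcting whether or not the covariate is adopted. NVPTQ Performance is an MMRM in the protocol and an ANCOVA in the SAP, and SAP Appendix 2 does not list the change. SAP 5.4.2 also uses the number 4 for both this endpoint and the DCIVA endpoint, which is number 5 in its own list.

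**What to change.** Before unmasking, add baseline mesopic, high contrast, binocular DCNVA in letters as one continuous covariate in the SAP 5.4.2 models for H5 and H9, and optionally for H10 and H11. Keep the four stratification factors and the baseline questionnaire score.

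In the same edit:

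- State one model for NVPTQ Performance, reconcile Protocol 9.4.1.3 with SAP 5.4.2, and record the change in SAP Appendix 2. If the MMRM is kept, the covariate goes into that model.
- Correct the DCIVA endpoint number in SAP 5.4.2.
- Give a rule for a missing covariate, for example the overall baseline mean with arms pooled.

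The cost is one degree of freedom. With 400 participants and seven parameters (intercept, treatment, four two-level factors, baseline score), the ANCOVA has at most 393 residual degrees of freedom. No new data are needed. SAP 5.1 already excludes site 051, where baseline DCNVA was measured with the wrong correction, from the efficacy analyses, so those readings would not enter the covariate.
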